##### **4.8.1. Escalation and Continuation Rules for Cohort A**

Subjects in Cohort A will receive 3,000 mg of ManNAc BID for 7 days before they are escalated to receive 6,000 mg BID for the rest of the trial:

[figure not shown]
- a. Subjects in Cohort A will be escalated to 6,000 mg BID on Day 7 if no serious AEs and no more than 2 Grade 2 drug-related AEs occur.
- b. If subjects experience  $\geq 2$  Grade 2 drug-related AEs or  $\geq 1$  drug-related SAE at 3,000 mg BID, the SRC will be convened to make escalation/de-escalation decisions based on Table 5.
- c. The subjects will continue on 6,000 mg BID until they experience  $\geq 2$  Grade 2 drug-related AEs or  $\geq 1$  drug-related SAE. In this case, the SRC will be convened to make decisions based on Table 5.

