##### **4.8.2. Initiation and Continuation Rules for Cohort B**

The SRC will review all available safety data for Cohort A of subjects prior to making a decision to initiate Cohort B. The SRC will convene when at least 14 days of safety have been collected on the last subject dosed in Cohort A.

- a. Cohort B will be initiated at 6,000 mg BID provided that there are  $< 2$  subjects in Cohort A that experienced  $\geq 2$  Grade 2 drug-related AEs or  $\geq 1$  drug-related SAE.
- b. If subjects experience  $\geq 2$  Grade 2 drug-related AEs or  $\geq 1$  drug-related SAE, the SRC will be convened to make decisions based on Table 6.

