**Figure 6. Dosing Escalation/De-escalation**

Table 6. Dose Escalation/De-escalation Rules	
Safety Profile*	Safety Review Committee Decisions*
No SAEs and Any number of CTCAE Grade 1 drug-related AEs or ≤ 1 CTCAE Grade 2 drug-related AE	Continue per protocol
2 CTCAE Grade 2 drug-related AEs	Continue per protocol, or study a lower dose § ,
≥ 3 CTCAE Grade 3 drug-related AEs	Study a lower dose § , or Withdraw the subject, and Convene SRC to evaluate the risk/benefit profile for dose escalation of other subjects
Any CTCAE Grade 4 AE; or ≥ 1 drug-related SAE Determination that the limit of safety and/or tolerability has been reached	Withdraw the subject, and Evaluate the risk/benefit profile in other subjects for dose escalations to or above the dose resulting in Grade 3 toxicity, and Discontinue study if 2 subjects develop the same Grade 3 toxicity or if any subject develops a Grade 4 toxicity

The safety decisions in this table apply only to safety and tolerability in an individual subject. If a decision is made that the dose escalation stopping criteria have been met, this does not preclude the use of the remaining subjects to evaluate the safety, PK, and PD effects of lower doses of ManNAc with the assessments described in this protocol.
 
*Note: Subjects from both Cohort A and Cohort B on 6,000 mg BID count toward the number of subjects experiencing toxicity.
 
§ Lower doses to study may include 4,500 mg BID, 3,000 mg BID or 2,000 mg BID depending on dose level where toxicity occurred.
	

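### For a subject with at most one Grade 2 AE, the dosing rules conflict at three or more non-serious Grade 3 AEs (Cohort A) and set no count trigger at one or two

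*Combined protocol and SAP*

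**What the plan says.** **Continuation triggers.** For Cohort A, 4.8.1(c) reads "The subjects will continue on 6,000 mg BID until they experience" two or more Grade 2 drug-related AEs or one or more drug-related SAEs, after which the SRC meets. For Cohort B, 4.8.2(b) uses the same counts to convene the SRC but has no wording that dosing continues until then. Section 4.9 convenes the SRC at more than two Grade 2 drug-related AEs, or when Grade 1 or 2 drug-related AEs limit tolerability. None of the three names Grade 3.

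**Table 6, rows counted from the top.**
- Row 1: no SAE, with Grade 1 AEs or at most one Grade 2 AE. The subject carries on as planned.
- Row 2: two Grade 2 AEs. Carry on, or a lower dose.
- Row 3: "≥ 3 CTCAE Grade 3 drug-related AEs". A lower dose or withdrawal, and the SRC meets about the other subjects.
- Row 4: any Grade 4 AE, a drug-related SAE, or a judgement that tolerability has reached its limit. The subject is withdrawn. The same cell holds a study-level clause: "Discontinue study if 2 subjects develop the same Grade 3 toxicity or if any subject develops a Grade 4 toxicity".

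**Scope of the table.** Its footnote states: "The safety decisions in this table apply only to safety and tolerability in an individual subject". Its asterisked note states: "Subjects from both Cohort A and Cohort B on 6,000 mg BID count toward the number of subjects experiencing toxicity".

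**Cross-references.** Section 4.8.1(b) says "the SRC will be convened to make escalation/de-escalation decisions based on Table 5", and 4.8 and 4.8.1(c) also point to Table 5. Section 4.8.2(b) reads "drug-related SAE, the SRC will be convened to make decisions based on Table 6". Table 5 is the visit schedule in section 4.3.

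**The concern.** Subject-level dosing rules should give one answer for any pattern of toxicity, and a worse pattern should not meet fewer triggers than a milder one. Here two Grade 2 drug-related AEs send a subject to the SRC by count, while two Grade 3 drug-related AEs with no Grade 2 AE do not. At three Grade 3 AEs, the section that staff happen to follow decides whether a Cohort A subject stays on dose.

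The study-stopping clause has a similar problem. It counts two subjects, but it sits in a row entered by other events and in a table that limits itself to one subject. Two readers could disagree on whether it has been met.

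Non-serious Grade 3 events do occur in this study. Section 3.8.2.2 reports one Grade 3 hypertriglyceridemia judged probably related to ManNAc, and no SAEs.

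**Working it through.** No sample size or error rate is involved, so the check sets the rules side by side.

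**Rules as coded, for one subject with no SAE and no Grade 4 AE.** Let a be the number of Grade 2 drug-related AEs and b the number of non-serious Grade 3 drug-related AEs.
- 4.8.1(c) and 4.8.2(b): triggered if a ≥ 2.
- 4.9 (count part): triggered if a > 2.
- Table 6: row 1 if a ≤ 1; row 2 if a = 2; row 3 if b ≥ 3.
- Row 4's tolerability entry and 4.9's tolerability clause are judgements, so they are left out of the counts.

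**A result that needs no grid.** With a = 0 or 1, no value of b meets 4.8.1(c), 4.8.2(b) or 4.9, because b does not enter them.

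| a | b | 4.8.1(c) / 4.8.2(b) | 4.9 count | Table 6 |
|---|---|---|---|---|
| 0–1 | 1–2 | not met | not met | no row names it |
| 0–1 | 3 | not met | not met | row 3 |
| 2 | 1–2 | met | not met | row 2 |
| 2 | 3 | met | not met | rows 2 and 3 |
| 3–4 | 0–2 | met | met | no row |
| 3–4 | 3 | met | met | row 3 |

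**Illustrative grid.** Take a = 0 to 4 and b = 0 to 3: 5 × 4 = 20 profiles, of which 5 × 3 = 15 have a Grade 3 AE. The grid is unweighted; it shows coverage, not how often a profile would occur.
- No count trigger: a in {0, 1}, b in {1, 2, 3}, so 2 × 3 = 6 of 15. The other 9 do meet one.
- Of those 6, b = 3 gives 2. These are the direct conflict in Cohort A: 4.8.1(c) continues and row 3 does not. In Cohort B they are a gap, because 4.8.2(b) does not say that dosing continues.
- The other 4 (b = 1 or 2) have no row that names them. Row 1 does not expressly exclude Grade 3, but it describes milder events.
- Referred to the table by 4.8.1(c)/4.8.2(b) but matching no row: a in {3, 4}, b in {0, 1, 2}, so 2 × 3 = 6 of 20. All six meet the 4.9 count, so only 4.9 supplies an action.

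**Other readings.**
- If Grade 2 means Grade 2 or higher, the trigger becomes a + b ≥ 2. The conflict at three disappears. Only (0, 1), a single Grade 3 AE, stays without a trigger: 1 of 15.
- If row 3 was meant to say Grade 2, the conflict at three disappears and three or more Grade 2 AEs gain a row. The same 6 of 15 still meet no count trigger.

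**Stopping clause.** Two subjects with one matching Grade 3 AE each satisfy its words. Each is 3 − 1 = 2 events short of row 3, and neither enters row 4 by count.

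**The case against.** **Judgement covers the gap.** Several routes do not depend on counts:
- review by the investigator, and by the SRC when safety issues arise (4.8);
- row 4's tolerability entry;
- withdrawal for medical reasons and sponsor termination for unacceptable risk (5.9);
- continuing SRC review (12.1.2) and SRC authority over the protocol (12.3.1);
- yearly DSMB review of AEs (12.3.2).

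This stands as far as it goes. A reader might infer that Grade 3 events have no safeguard, and the documents do not support that. But discretion does not settle two written rules with different outcomes, and the earlier DSMB review in 12.3.2 needs a drug-related SAE.

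**The conflict depends on the reading.** True: it needs both Grade 2 in the triggers and Grade 3 in row 3 to be taken literally. Under either alternative, at least a single Grade 3 AE still has no count trigger.

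**The reported case.** A reader might infer that the subject with hypertriglyceridemia fell into the gap or was handled wrongly. Neither 3.8.2.2 nor 9.1.1 gives that subject's cohort or Grade 2 count. Gastrointestinal problems affected 8 of 12 subjects, so a Grade 2 trigger may already have been met.

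**Row 1.** A reader might say that the table tells staff to carry on after one or two Grade 3 AEs. That stretches a row written for Grade 1 and Grade 2 events; the fairer description is that no row clearly applies.

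**Matters left aside.** Section 4.8.1(a) escalates "if no serious AEs and no more than 2 Grade 2 drug-related AEs occur", which overlaps with 4.8.1(b) at exactly two Grade 2 AEs. Those Day 7 decisions are past, since SRC review already covers 24 months. Whether subjects on a reduced dose or on the later three-times-daily dosing count under the table's note is missing detail, not a contradiction. The different counts in 4.9 (more than two) and 4.8.1(c) (two or more) are inconsistent thresholds, not contradictory instructions.

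**Conclusion.** The inconsistency is real, within stated limits. It concerns a single subject with at most one Grade 2 drug-related AE and neither an SAE nor a Grade 4 AE, under a literal reading. There, three or more non-serious Grade 3 AEs produce a direct conflict in Cohort A and a gap in Cohort B, and one or two leave only judgement. It does not extend to every Grade 3 pattern: 9 of the 15 grid profiles do meet a count trigger.

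Three further faults do not depend on the meaning of Grade 2 in the triggers:
- As printed, the table has no row for three or more Grade 2 AEs with fewer than three Grade 3 AEs.
- The study-stopping clause is placed where its own condition does not lead.
- Sections 4.8 and 4.8.1 cite the wrong table.

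Figure 6 is not visible in the text supplied and Table 6 has lost its layout, so the row findings rest on the extracted wording. The figure could clarify the rows, but it would not alter the wording of 4.8.1(c). Because these rules govern dosing and study stopping, they should be reconciled even though much of the follow-up is complete.

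**What to change.** The sponsor and SRC should:
1. Reconcile 4.8.1(c), 4.8.2(b), 4.9, Table 6 and Figure 6 so that each combination of Grade 2, 3 and 4 AEs and SAEs leads to one consistent decision path. SRC options can remain within a path.
2. Confirm whether the grade in row 3 is as intended.
3. Separate the study-level stopping rule from the individual-subject rules.
4. Change the Table 5 references in 4.8 and 4.8.1 to Table 6.

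Which thresholds and dose actions apply is for the sponsor and SRC to decide; this review takes no view. The cost is amendment wording only, with no added patients, visits or data.

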##### **4.8.2. Initiation and Continuation Rules for Cohort B**

The SRC will review all available safety data for Cohort A of subjects prior to making a decision to initiate Cohort B. The SRC will convene when at least 14 days of safety have been collected on the last subject dosed in Cohort A.

- a. Cohort B will be initiated at 6,000 mg BID provided that there are  $< 2$  subjects in Cohort A that experienced  $\geq 2$  Grade 2 drug-related AEs or  $\geq 1$  drug-related SAE.
- b. If subjects experience  $\geq 2$  Grade 2 drug-related AEs or  $\geq 1$  drug-related SAE, the SRC will be convened to make decisions based on Table 6.

**Figure 6. Dosing Escalation/De-escalation**

Table 6. Dose Escalation/De-escalation Rules	
Safety Profile*	Safety Review Committee Decisions*
No SAEs and Any number of CTCAE Grade 1 drug-related AEs or ≤ 1 CTCAE Grade 2 drug-related AE	Continue per protocol
2 CTCAE Grade 2 drug-related AEs	Continue per protocol, or study a lower dose § ,
≥ 3 CTCAE Grade 3 drug-related AEs	Study a lower dose § , or Withdraw the subject, and Convene SRC to evaluate the risk/benefit profile for dose escalation of other subjects
Any CTCAE Grade 4 AE; or ≥ 1 drug-related SAE Determination that the limit of safety and/or tolerability has been reached	Withdraw the subject, and Evaluate the risk/benefit profile in other subjects for dose escalations to or above the dose resulting in Grade 3 toxicity, and Discontinue study if 2 subjects develop the same Grade 3 toxicity or if any subject develops a Grade 4 toxicity

The safety decisions in this table apply only to safety and tolerability in an individual subject. If a decision is made that the dose escalation stopping criteria have been met, this does not preclude the use of the remaining subjects to evaluate the safety, PK, and PD effects of lower doses of ManNAc with the assessments described in this protocol.
 
*Note: Subjects from both Cohort A and Cohort B on 6,000 mg BID count toward the number of subjects experiencing toxicity.
 
§ Lower doses to study may include 4,500 mg BID, 3,000 mg BID or 2,000 mg BID depending on dose level where toxicity occurred.
	

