#### **4.8. Dose Escalation**

Subjects in Cohort A will receive 3,000 mg of ManNAc BID for 7 days before they are escalated on Day 7 to receive 6,000 mg BID for the rest of the trial. The evaluation of a dose escalation/de-escalation for an individual will initially be reviewed by the Principal Investigator, according to the criteria in Table 5 and reviewed by the Safety Review Committee (SRC) when the Cohort is completed or safety issues arise. The safety information to be reviewed will include AEs, physical exams, vital signs, and clinical laboratory data.

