#### **4.9. Dose Modification**

If a subject experiences >2 Grade 2 drug-related AE's or any Grade 1 or Grade 2 drug-related AE's that limit tolerability, the SRC will be convened and dose modification considered with a goal of improving tolerability.

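### Table 6 stops the study at two subjects with the same Grade 3 toxicity, but its note limits the table to individual subjects and its rows leave most Grade 3 events unplaced

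*Combined protocol and SAP*

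**What the plan says.** Table 6 (Dose Escalation/De-escalation Rules) pairs four safety profiles with SRC decisions. The last row is entered by any Grade 4 event, by at least one drug-related serious adverse event (SAE), or by "Determination that the limit of safety and/or tolerability has been reached". Its decision cell withdraws the subject, calls for a risk/benefit review for others, and ends with the instruction "Discontinue study if 2 subjects develop the same Grade 3 toxicity or if any subject develops a Grade 4 toxicity".

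Two notes follow. The unmarked note states: "The safety decisions in this table apply only to safety and tolerability in an individual subject". It adds that if escalation stopping criteria are met, "this does not preclude the use of the remaining subjects to evaluate the safety, PK, and PD effects of lower doses of ManNAc". The asterisk note, keyed to both column headings, states: "Subjects from both Cohort A and Cohort B on 6,000 mg BID count toward the number of subjects experiencing toxicity".

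Row 3 is entered at or above "3 CTCAE Grade 3 drug-related AEs" and leads to a lower dose or withdrawal, with the SRC convened. Section 4.9 calls the SRC and considers dose modification on a similar count at a different grade: "If a subject experiences >2 Grade 2 drug-related AE's". Section 4.8 has the SRC review dose decisions "when the Cohort is completed or safety issues arise".

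Sections 3.8.2.2 and 9.1.1 report one Grade 3 hypertriglyceridemia, probably related to ManNAc, and no SAEs through 24 months.

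**The concern.** A rule that ends a trial should give one answer to anyone who applies it. Here the instruction counts two subjects and acts on the study, while the note confines the table to one subject at a time. The instruction also sits in a row that two ordinary Grade 3 cases do not enter on grade alone. Separately, row 3 breaks the run of Grade 2 counts above it, which leaves gaps at three Grade 2 events and at one or two Grade 3 events.

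What is at stake is patient-safety wording, not an estimate or an error rate. If a second subject develops the same Grade 3 toxicity, the committee would have to settle what its own rule means while deciding whether to apply it.

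**Working it through.** The documents give no operating characteristics for this rule, so there is no figure to reproduce. The check is to run cases through the table.

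| Row | Entry condition (paraphrased) | Names Grade 3 at entry? | Study stop? |
|---|---|---|---|
| 1 | No SAE; any Grade 1, or at most 1 Grade 2, drug-related | No | No |
| 2 | Exactly 2 Grade 2, drug-related | No | No |
| 3 | At least 3 Grade 3, drug-related | Yes | No |
| 4 | Any Grade 4; or at least 1 drug-related SAE; or a determination that the limit is reached | No | Yes |

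Rows that both name Grade 3 at entry and carry the stop: 0 of 4.

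**Case A: two subjects on 6,000 mg BID, each with one drug-related, non-serious Grade 3 event of the same type.**
- Stop clause's own count: 2 observed, 2 needed. Met.
- Rows 1 and 2 list only Grades 1 and 2, so they do not address the case.
- Row 3 needs 3. There is 1 per subject and 1 + 1 = 2 in all. Not met on either count.
- Row 4: Grade 4 events 0, SAEs 0. Entry only if the committee makes the discretionary determination.
- Scope note: individual subject only.

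The clause says stop, row entry depends on judgement, and the note says the decision does not reach beyond the subject.

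**Case B: one subject with three drug-related Grade 2 events, no SAE.**
- Row 1 allows at most 1, and 3 > 1. Row 2 needs exactly 2. Row 3 needs Grade 3, and there are 0. Row 4 has no matching grade condition.
- No grade-based row fits. Section 4.9 does catch the case, since 3 > 2, but Table 6 does not.
- If row 3 read Grade 2, the table would run at most 1, then 2, then at least 3. For whole numbers, at least 3 is the same as more than 2, so it would also match Section 4.9. This is why a misprint is likely.

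**Case C: one subject with one or two drug-related, non-serious Grade 3 events.**
- Row 3 needs 3. Row 4 needs Grade 4, an SAE or the determination. No grade-based row fits.
- The triggers for convening the SRC in Sections 4.8.1 and 4.8.2 name Grade 2 events and SAEs. Section 4.9 names Grades 1 and 2. None names Grade 3.
- If row 3 is corrected to Grade 2 and nothing else changes, non-serious Grade 3 events of any number fit no grade-based row. The correction therefore needs a Grade 3 row alongside it.

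**Current tally.** One Grade 3 event is reported, and with no SAEs reported it was non-serious. If it counts, the study is 2 − 1 = 1 subject short of the stop. The dose at onset is not given.

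**Elsewhere.** No other section restates the two-subject count. Section 7.4 lists interim analyses without a stopping criterion.

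**The case against.** The strongest reply is that the stop clause contains its own complete trigger. It counts two subjects, so it cannot be a decision about one. The asterisk note pools both cohorts, which makes sense only if a study-level count was meant. A sensible committee member would let the specific clause prevail over the general scope sentence. This stands as the natural reading of intent. It does not make the scope sentence correct, because that sentence says the table applies only to individuals.

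It is also fair that the last row deals with Grade 3 in its decision cell, and that the table was read from a PDF, so the division of the entry cells could have been disturbed. The order of the decision lines in the table of contents agrees with the layout, but it says nothing about the entry cells. Figure 6 is not visible and may route Grade 3 events.

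Backstops exist and have weight. The SRC reviews safety on an ongoing basis (12.1.2) and decides on termination (12.3.1). The sponsor must terminate for unacceptable risk (5.9). The DSMB reviews all events yearly, and sooner after a drug-related SAE (12.3.2). None of them sets a count.

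A reader might infer that the note's second sentence lets the study carry on at lower doses after the stop has fired. The text does not support that: it speaks of criteria for stopping dose escalation, which most naturally differs from discontinuing the study. A reader might also take the asterisk note to mean that only events at 6,000 mg BID count. It says those subjects count; it does not clearly exclude events at a reduced dose.

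**Conclusion.** Wrong as written, and it should be fixed. The stop and the scope sentence contradict each other. None of the three entry conditions of the row holding the stop names Grade 3, and one of the three can admit it by judgement. Row 3 is probably a misprint; as printed it leaves Cases B and C without a grade-based row.

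The conclusion assumes that the extracted row layout is faithful and that Figure 6 does not resolve the point. It makes no claim about the probability of a second event.

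A reader might go further and infer that the trial lacks a study-level stopping rule, or that subjects are unprotected against repeated Grade 3 toxicity. The documents do not support either: the clause and the asterisk note show the intent, and the SRC, DSMB and sponsor can all act. Nor do they show that the rule has been met or breached. One event is reported, and whether it counts toward the two depends on how the asterisk note is read and on a dose at onset that is not stated.

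**What to change.** 1. Confine the individual-subject sentence to the individual-level decisions. State the study stop as a standalone rule outside the rows: discontinue if two subjects, Cohorts A and B counted together, develop the same Grade 3 toxicity, or if any subject develops a Grade 4 toxicity. Do not word it so that Grade 3 events at reduced doses drop out; Section 9.1.1 already reports one dose reduction.
2. Correct row 3 to three or more Grade 2 drug-related events, or confirm that Grade 3 is meant.
3. Add a row for a single drug-related Grade 3 event: lower dose or withdraw the subject, with SRC review.

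The cost is protocol wording plus an occasional SRC meeting. No visits, tests or subjects are added.

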#### **4.9. Dose Modification**

If a subject experiences >2 Grade 2 drug-related AE's or any Grade 1 or Grade 2 drug-related AE's that limit tolerability, the SRC will be convened and dose modification considered with a goal of improving tolerability.

#### **4.10. Subject Compliance**

Subjects will have directly observed therapy of drug doses administered while inpatient. CC nursing staff will document doses in CRIS.

A diary will be provided to subjects so that AEs, compliance, concomitant medications and other issues can be recorded during the treatment phase while they are at home ([Appendix K](#)). The diary will be in paper format, and will be reviewed by a member of the study team during every study visit.

Adverse events, compliance with study procedures, concomitant medications and other issues will also be recorded by a member of the study team during the treatment phase on CRFs.

